9.1.1 Schedule of Events

Table 1 Data Collection/Observation

	Data Collection/Observation	Baseline ^a ± 7 days	Week 12 (V2) ± 7 days	Week 24 (V3) ± 7 days	Early Termination / Drop out	70 days after the Week 24 or the last dose	150 days after the Week 24 or the last dose
Clinician Packet	Inclusion/exclusion form	X					
	Clinical history/patient demographics	X					
	Comorbidities	X					
	DAS28 (ESR) or DAS28 (CRP)	X	X	X	X		
Patient Packet	EuroQoL 5-Dimension (EQ-5D)	X	X	X	X		
	Short Form 36-Item Health Survey (SF-36)	X	X	X	X		
	Health Assessment Questionnaire (HAQ)	X	X	X	X		
	Work Productivity and Activity Impairment Questionnaire (WPAI)	X	X	X	X		
	Healthcare Resource Utilization (HCRU)	X	X	X	X		
	Patient Global Impression of Change (PGIC)		X	X	X		
	Patient Treatment Satisfaction Questions	X	X	X	X		
Clinicia	Adverse events	←				→	
	Pregnancy	←				→	

a. The Baseline will serve as the reference date for all subsequent time-points. A ± 7 day window is permitted around scheduled data collection time-points.

9.2

Setting

The study will take place in single country (Taiwan) with multiple centers. The study sites will be identified and selected by AbbVie. The study population shall comprise of male and/or female patients who are attending a routine clinical visit and meet all of the inclusion criteria and none of the exclusion criteria. Overall, approximately 100 subjects with clinically diagnosed RA are planned to be enrolled in the study at up to 7 sites.

The recruiting investigators will select potentially eligible patients from consecutive visits within their clinic based on the inclusion and exclusion criteria (Section 9.2.1 and Section 9.2.2). It is the responsibility of each physician to ask every consecutive patient who meets the inclusion criteria of the study to participate to avoid selection bias, and if investigators hold different types of clinics (e.g. routine visit clinics versus emergency clinics), only patients visiting their routine clinics will be used for patient selection.

Site personnel should thoroughly assess the eligibility criteria and evidence of this should be stored with the source documentation at site. Where there is any deviation from the inclusion/exclusion criteria, the patient should be excluded from the study.

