Subjects that initially screen fail for the study may be permitted to re-screen following re-consent. All screening procedures with the possible exceptions noted below will be repeated. The subject must meet all inclusion and none of the exclusion criteria at the time of re-screening in order to qualify for the study. There is no minimum period of time a subject must wait to re-screen for the study. If the subject had a complete record of eligible criteria including a PPD test (or equivalent), or Interferon-Gamma Release Assay (IGRA; QuantiFERON-TB Gold In-Tube test or T-SPOT TB test), Chest x-ray (if applicable) and ECG no more than 3 months (90 days) have passed, these data will not be required to be repeatedly collected for re-screening. As appropriate, sites are encouraged to contact the AbbVie Medical Monitor to confirm if subjects should or should not be re-screened.

9.2.1 Inclusion Criteria:

Patients meeting all of the following inclusion criteria at baseline will be included:

1. Subject has a diagnosis of RA as defined by the 1987 revised ACR classification criteria and/or the ACR/ the European League against Rheumatism (EULAR) 2010 classification criteria (any duration since diagnosis)
2. Male or female subjects ≥ 18 years of age (local definition according to adalimumab label) who is in compliance with eligibility for adalimumab based on the local label
3. Patients with moderate to severe RA defined as DAS28 (ESR) or DAS28 (CRP) > 3.2

4. Biologically treatment naïve and initiated adalimumab at baseline visit
5. Availability of clinical data of the previous 12 weeks prior to baseline
6. Ability to self-complete patient questionnaires
7. Subject must be able and willing to provide written informed consent and comply with the requirements of this study protocol

Additional Inclusion Criteria

8. Female subjects who are either not of childbearing potential, defined as postmenopausal for at least 1 year or surgically sterile (bilateral tubal ligation, bilateral oophorectomy and/or hysterectomy) or are of childbearing potential and are practicing an approved method of birth control throughout the study and for 150 days after the Week 24 dosing or the last dose of adalimumab.

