9.2.4.7 Study Documents

Clinical case report form (CRF)

The clinical CRF will document the patient's current status (moderate, severe RA), Disease Activity Score in 28 joints (DAS28), prior and current treatments and other relevant clinical and demographic data to be used in segmenting the population during analysis.

To calculate the DAS28 the physician or specialist nurse will:

1. Count the number of swollen joints (out of the 28)
2. Count the number of tender joints (out of the 28)
3. Record the blood test data of erythrocyte sedimentation rate (ESR) or C reactive protein (CRP) using the latest measurement in the medical records
4. Record the 'global assessment of health' of patients, which will be indicated by marking a 10 cm line between very good and very bad

The physician or specialist nurse will then mark each component score on the CRF and the DAS28 score if calculated (an online scoring calculator for the DAS28 can be found at [REDACTED])

The DAS28 will be scored using the following formula:

$$\text{DAS28 ESR} = 0.56 * \text{sqrt}(\text{tender28}) + 0.28 * \text{sqrt}(\text{swollen28}) + 0.70 * \ln(\text{ESR}) + 0.014 * (\text{Global assessment of Health in cm})$$

$$\text{DAS28 CRP} = 0.56 * \text{sqrt}(\text{tender28}) + 0.28 * \text{sqrt}(\text{swollen28}) + 0.36 * \ln(\text{CRP}) + 0.014 * (\text{Global assessment of Health in cm}) + 0.96$$

DAS28 scores will be interpreted using the following categorization:

- Remission: $DAS28 \leq 2.6$
- Low Disease activity: $2.6 < DAS28 \leq 3.2$
- Moderate Disease Activity: $3.2 < DAS28 \leq 5.1$
- High Disease Activity: $DAS28 > 5.1$

The full CRF is presented in Appendix C.

PRO questionnaires

The following PRO questionnaires will be included in the patient questionnaire packet.

Health Assessment Questionnaire Disability Index (HAQ DI)

The HAQ DI is a patient-reported questionnaire to assess functioning impacted by RA. It includes the categories of dressing and grooming, arising, eating, walking, hygiene, reach, grip and common daily activities. It asks patients about the amount of difficulty they experience in these activities as well as the use of aids and/or devices. The HAQ also has a numeric rating scale (NRS) (13) to assess pain on a scale from 0 to 10. Self-administered by the patient, the completion time is approximately 3-4 minutes. The full version of HAQ DI is presented in Appendix D.

Short Form (36) Health Survey (SF-36)

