All of the following information must be completed by the clinician or his/her representative.

Clinician name: _____

Clinician signature: _____

[figure not shown]
[figure not shown]
Site & participant ID

Today's date: / /

Please provide the information below.		
1. What is the patient's current disease status?	 Moderate	 Severe

1023259 Real-World Impact of RA

100

Please provide the information below.
 
2. Please perform a swollen and tender joint examination on your patient using the figure below and record the total number of tender/swollen joints in the appropriate boxes on the right.
		 	Tender Joint Count	 	Swollen Joint Count

If diagnosis is RA:
 
 
  
 
  
 
					

3. Please record the most recent Erythrocyte Sedimentation Rate (ESR) (in mm/hour) or C-reactive protein (CRP) (in mg/L) of this patient.
			
   ESR (mm/hour)
 
   CRP (mg/L)
		

4. Please record the latest DAS28 score*, if calculated
					

* For calculation instruction, please refer to study protocol, page 21, clinical case report form (CRF).

1023259 Real-World Impact of RA
[Site number] - [Participant ID]

[figure not shown]
5. Please check all the surgeries this patient has received for her/his Rheumatoid Arthritis since the last completed survey.			
 No surgery performed			
 Yes →	Type of Surgery (Please input the number of the list below)	Length of Stay*	Date of surgery (DD/MM/YYYY)
	 1 _____	_____ days	_____/_____/_____
	 2 _____	_____ days	_____/_____/_____
	 3 _____	_____ days	_____/_____/_____
	 4 _____	_____ days	_____/_____/_____
	 5 _____	_____ days	_____/_____/_____
List of common surgeries for rheumatoid arthritis:			

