5.5 Analysis Plan for Exploratory Objectives

- Excel Table 7 describes the change in 4 patient satisfaction questions at weeks 12 and 24 after the initiation of adalimumab, in those patients continuing on adalimumab (observed population). These changes will be summarized as number and percentage of each response and compared with Wilcoxon signed rank test shown by p-value1. Satisfaction will also be dichotomized and analyzed over time with Cochran-Armitage test for trends shown by p-value2 in the table.
- Excel Table 8 summarizes the patients' global impression of change in RA at weeks 12 and 24 after the initiation of adalimumab, in those patients continuing on adalimumab (as observed population). Each response (very much better, much better, a little better, no change, a little worse, much worse, and very much worse) will be summarized as number and percentage.
- Descriptive statistics will be presented for post-index overall RA related direct healthcare resource utilization (Excel Table 9)
 - Consultations/visits to healthcare professionals for treatment of RA (number of patients with ≥ 1 visit; categorized by the treatment department listed in 3.5.4)
 - Procedures received when visiting the healthcare professional(s) for treatment of RA (number of patients with ≥ 1 procedure; categories listed in 3.5.4)
 - surgeries received when visiting the healthcare professional(s) for treatment of RA (number of patients with ≥ 1 surgery; categories listed in 3.5.4)
 - Hospitalizations in relation to RA (number of patients with ≥ 1 admission)
 - Length of stay in days (mean, SD, median)
 - Concomitant medications taken for RA (number of patients with ≥ 1 medication; categories listed in 3.5.4))
- Associations between disease severity (measured by DAS28) and PROs (HAQ DI score, SF-36 domain scales, EQ-5D-3L index, WPAI outcomes) will be analyzed using the bivariate linear regression model (Excel Table 10.1). Separate models will be estimated to identify the association between DAS28 and each of the PROs.
- Additionally, in Excel Table 10.2, separate bivariate liner regression models will be estimated to identify the association between change in DAS28 and change in each of the PROs at 12 and 24 weeks after baseline respectively.

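### DAS28-ESR and DAS28-CRP are interchangeable at every visit under one set of cut-offs, so severity class and DAS28 change partly reflect which marker was used

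*Protocol*

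**What the plan says.** Protocol 9.2.1, criterion 3, admits "Patients with moderate to severe RA defined as DAS28 (ESR) or DAS28 (CRP) > 3.2". Table 1 in 9.1.1 repeats the choice of version in a single row covering baseline, Week 12, Week 24 and early termination. Protocol 9.2.4.7 tells the assessor: "Record the blood test data of erythrocyte sedimentation rate (ESR) or C reactive protein (CRP) using the latest measurement in the medical records". The baseline, follow-up and early-termination clinician forms each ask: "Please record the most recent Erythrocyte Sedimentation Rate (ESR) (in mm/hour) or C-reactive protein (CRP) (in mg/L) of this patient". They have separate ESR and CRP boxes and one box for the latest DAS28, if calculated. The forms as extracted show no field for the version of that score.

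Protocol 9.2.4.7 then gives two formulas. The joint-count and global terms are the same. The marker part is 0.70 ln(ESR) in one, and 0.36 ln(CRP) plus a constant of 0.96 in the other. One set of cut-offs (2.6, 3.2, 5.1) serves both. SAP 3.5.2 keeps those cut-offs but has a single formula, with 0.70 applied to the log of whichever marker is used and no constant.

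Severity class or DAS28 feeds these analyses:
- the severity-adjusted ANOVA (protocol 9.7.4 and 9.7.5, SAP 5.3);
- the moderate/severe subgroups (protocol 9.7.3);
- SAP Table 10.1 (DAS28 against each PRO);
- SAP Table 10.2, which estimates the "association between change in DAS28 and change in each of the PROs at 12 and 24 weeks after baseline respectively";
- the modifier models in SAP Table 11.

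Neither document ties a patient to one version, or says which counts when both markers are on file.

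**The concern.** Two scores with different marker weights and a different constant are treated as one variable. This has two consequences.

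First, two patients with the same joints, global assessment and blood results can fall in different severity classes because their sites use different markers.

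Second, a patient scored on one marker at baseline and the other at Week 12 or 24 shows a DAS28 change that is partly, or wholly, the change of formula. In a regression of PRO change on DAS28 change, that acts as measurement error in the explanatory variable and flattens the slope.

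The problem is separate from the age of the blood value and from the SAP's conflicting formula. It remains with fresh values and with the protocol's own weights.

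**Working it through.** The plan states no figure for the gap, so there is none to reproduce. The formulas are those in protocol 9.2.4.7, with ESR in mm/h and CRP in mg/L.

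**Gap between versions.** Joint counts and global assessment cancel, leaving

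D = DAS28-ESR − DAS28-CRP = 0.70 ln(ESR) − 0.36 ln(CRP) − 0.96.

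The only ESR/CRP pair in the documents is the pair of reimbursement thresholds in protocol section 7.0 (25 mm/h and 1 mg/dL, that is 10 mg/L). These are policy limits, not patient data. All other pairs below are assumed.

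| ESR | CRP | D, protocol formulas |
|---|---|---|
| 25 | 10 | 2.253 − 0.829 − 0.96 = 0.46 |
| 28 | 10 | 0.54 |
| 30 | 10 | 0.59 |
| 40 | 15 | 0.65 |
| 30 | 5 | 0.84 |
| 20 | 20 | 0.06 |
| 50 | 5 | 1.20 |
| 10 | 20 | −0.43 |

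Over the whole grid of ESR 20–50 and CRP 5–20, D runs from 0.06 to 1.20 with a median of about 0.6. About 47% of the grid lies between 0.5 and 0.8.

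**Effect on class.** Take ESR 30, CRP 10 and a global assessment of 5 cm, entered as the protocol writes it.
- 12 tender and 9 swollen joints: the common part is 0.56√12 + 0.28√9 + 0.014 × 5 = 2.85. The ESR version is 2.85 + 2.38 = 5.23 (above 5.1). The CRP version is 2.85 + 0.83 + 0.96 = 4.64 (moderate).
- 2 tender and 2 swollen joints: 3.64 against 3.05, on either side of 3.2.

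**Effect on change.** For the same marker values, moving from ESR at baseline to CRP later with no clinical change gives −0.59. For comparison, a real fall in ESR from 40 to 20 within one version contributes 0.70 ln(20/40) = −0.49.

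**Effect on Table 10.2.** Assume DAS28 change is the explanatory variable and its true SD is 1.2 (variance 1.44). Assume also that a proportion p of patients switch, with offset ±0.6 in either direction, independent of true change, plus noise SD 0.3 in switchers. The added variance is p(0.6² + 0.3²) = 0.45p, and the slope is multiplied by 1.44/(1.44 + 0.45p).

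| p | Multiplier | Shrinkage |
|---|---|---|
| 5% | 1.44/1.4625 | 1.5% |
| 10% | 1.44/1.485 | 3.0% |
| 25% | 1.44/1.5525 | 7% |
| 50% | 1.44/1.665 | 14% |

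**Under the SAP formula** the gap would be 0.70 ln(ESR/CRP): 0.77 at 30/10 (protocol 0.59) and 0.97 at 40/10 (protocol 0.79). The offset in the analysed data is not settled until the two documents agree.

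**Primary analysis and power.** The primary test is a paired t-test on HAQ DI change, unadjusted for severity. The power statements in protocol 9.5 use HAQ DI and hours of work lost. Recomputed, they give 97.6% and 96.4% with 90 patients and 62.8% with 49, in line with the stated 95% or more, 95% or more, and 63%. None involves DAS28.

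**The case against.** The strongest reply concerns size and reach. The documents give no patient marker values and no switching rate. The one pair they contain gives 0.46, the gap can reverse, and if only 5–10% of patients switch the slope loses 1.5–3%. DAS28 change is not an endpoint; it enters one exploratory regression. The forms already have separate boxes for the two markers, so the marker on file is largely visible. Taking values from routine records is deliberate in a non-interventional study. All of this stands, and it limits the point. It does not supply a rule for which version to use. Variation in the gap's size and sign also means that no single correction could remove it afterwards.

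A same-version rule has a price too. If 25–50% of patients switched and had no same-version value, dropping them would raise the standard error of the slope by about 15–41% (1/√0.75 and 1/√0.50). That can outweigh the bias removed.

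A reader might go further and infer that sites can retry a failed score with the other marker, because "There is no minimum period of time a subject must wait to re-screen for the study", and that patients are thus selected on a high reading, inflating the before-after HAQ DI change. The documents do not support this. The criterion is an either/or, so a patient above 3.2 on one available version qualifies at first screening without a retry. Re-screening requires new consent and, with limited exceptions, repeated procedures. A systematic offset between formulas is not a chance high reading: it lowers the effective threshold and lets in somewhat milder patients. No effect on HAQ DI has been shown.

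**Conclusion.** The point holds within limits. The plan accepts either version at entry and at each visit, applies common cut-offs to two different formulas, and has no rule for keeping or recording the version. Class near 5.1 therefore depends partly on the marker, and a version switch enters DAS28 change as false change.

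The gap follows from the protocol's formulas, but its size rests on assumed marker values: 0.06 to 1.20 on the grid, 0.46 at the only documented pair, and negative for some discordant values. It would be wrong to quote a narrow range as typical of these patients. The slope shrinkage of 1.5% to 14% rests on the assumed SDs, offset and switching rate.

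The reach is the severity-adjusted sensitivity ANOVA, the severity subgroups, and SAP Tables 10.1, 10.2 and 11. The clinician's own moderate/severe tick on the forms does not remove the dependence, because SAP 3.5.2 defines the classes by DAS28. The primary HAQ DI result and the sample size stand as they are.

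**What to change.** 1. Reconcile the single DAS28 formula in SAP 3.5.2 with the two formulas in protocol 9.2.4.7. The steps below depend on it.
2. In protocol 9.2.4.7 and SAP 3.5.2, record the version on the CRF. Use the baseline version for the severity class, and for all later visits where that marker is available. Compute DAS28 change for Table 10.2 only between scores of the same version. Add a sensitivity analysis of all patients with a version-switch indicator.
3. Add DAS28 version as a covariate in the severity-adjusted ANOVA and in Tables 10.1, 10.2 and 11. Keeping a patient on one version cannot remove version differences between patients, at entry or in class, so the covariate is needed as well. Report the number of patients by version and the number who switch.

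The cost is wording in two documents and one tick-box. Collection was planned to end on 31 January 2017 and the SAP's table-shell files carry January 2018 dates. If the forms are already complete, take the version from the ESR and CRP boxes wherever these identify it. Patients with no same-version follow-up value leave the main Table 10.2 analysis. The precision lost depends on the switching rate, which is why the all-patient sensitivity analysis and the switch count are needed. No sample size or power figure changes.

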9.2.3 Investigator Selection Criteria

Selection of investigators will be made based on qualification by training and experience. AbbVie will provide IMS with a list of clinicians that would be able to assist in recruiting in a timely manner. IMS will contact each clinician to obtain their participation in the study and provide an expected number of patients to be enrolled from that clinic. The ethical review boards recognized by the respective participating sites are required to review and approve the study and patient informed consent.

9.2.4 Study Procedures

The study procedures outlined in Table 1 will be discussed in detail in this section with the exception of adverse events procedures (discussed in Section 11.0).

9.2.4.1 Informed Consent

Following the current local regulations in Taiwan, informed consent forms (ICF; Appendix A) in local language will be given to every patient participating in the study before data collection commences. The recruiting clinicians or their representative(s) will provide each patient with the ICF to sign which includes consent to use the data for publication and information including their right to withdraw from the study without penalty or change in medical care the patient is otherwise entitled to.

Potential drug to drug interactions with oral contraceptives and need for alternative methods of birth control will be informed.

“If you are already using a method of birth control, you should check with the study doctor to make sure it is considered acceptable for this study. Certain drugs may interact with contraceptive agents and reduce their effectiveness, therefore you should inform the study doctor of all medications (prescription and over-the-counter) that you are currently taking or begin taking during the study.”

[figure not shown]
9.2.4.2 Patient Assignment

Once the recruiting clinician has obtained the subject’s authorization to release medical information and written consent to participate in the study, the clinician will be asked to complete an inclusion and exclusion form (

Appendix B) for patients, thus confirming the patient's eligibility to participate in this study.

Each participating patient will be assigned a 3-digit patient identification number. The numbers should be assigned in sequential, ascending order per site as shown below:

- Site ID; and
- Patient ID: First eligible patient number will be 001, and then the second patient number would be 002

9.2.4.3 Investigator Recruitment

AbbVie will provide IMS (CRO Division in IMS) with a list of clinicians that would be able to assist in recruiting in a timely manner. IMS will contact each clinician to obtain their participation in the study and provide an expected number of patients to be enrolled from that clinic. The ethical review boards recognized by the respective participating sites are required to review and approve the study and patient informed consent.

9.2.4.4 Study site monitoring

As the study entails patients completing PRO questionnaires and clinicians completing case report forms (CRFs), there is not a need for on-site monitoring visits. IMS will closely track enrolment progress for bi-monthly reporting. IMS will work closely with the study coordinator at each site to ensure they check the forms when returned from the patients and physicians (e.g., all questions were answered). IMS will also be available to answer questions and follow up with the sites if the recruitment process is slow or if there are any errors on the forms. Periodic phone follow-up will be conducted to ensure data collection completeness and quality.

9.2.4.5 Patient Selection

The recruiting investigators will select potentially eligible patients from consecutive visits within their clinic based on the inclusion and exclusion criteria (Section 9.2.1 and Section 9.2.2). It is the responsibility of each physician to ask every consecutive patient who meets the inclusion criteria of the study to participate to avoid selection bias, and if investigators hold different types of clinics (e.g. routine visit clinics versus emergency clinics), only patients visiting their routine clinics will be used for patient selection. The intent is to enroll patients who have been prescribed adalimumab upon the physicians' own discretion.

Medical and Surgical History

A detailed medical history with respect to TB exposure needs to be documented. This information needs to include BCG vaccination, cohabitation with individuals who have had TB, and/or who reside or work in TB endemic locations.

Physical Examination

Physical exam records at routine clinic visits will be collected at scheduled timepoints. Physical examination findings that are related or part of each subject's medical history should be captured on the appropriate eCRF page.

12-Lead Electrocardiogram (ECG)

Resting 12-lead ECG records will be collected at Baseline. A qualified physician will interpret the clinical significance of any abnormal finding, sign, and date each ECG. Any clinically significant findings will be documented in the source documents and later transcribed on to the appropriate eCRF.

For subjects with a normal ECG taken within 90 days prior to Baseline, a repeated ECG record before enrollment will not be required, provided all protocol required documentation is available. If there is any finding clinically significant, the Principal Investigator must contact the Medical Monitor before enrolling the subject.

Subjects can have a repeat ECG at any time during the study as warranted based on the opinion of the Investigator.

Chest X-ray (CXR)

A standard CXR (posterior-anterior [PA] and lateral views) report within 90 days prior to Baseline to rule out the presence of TB or other clinically relevant findings will be collected, provided all protocol required documentation is available at the site (as outlined below).

Subjects can have a repeated CXR at any time during the study as warranted based on the judgment of the Investigator. The Principal Investigator will indicate the clinical significance of any finding, including the presence or absence of (1) calcified granulomas, (2) pleural scarring/thickening, and (3) signs of active TB, and will sign and date the report.

Pregnancy Tests

At the Baseline Visit, subjects of childbearing potential should be confirmed as non-pregnant. A lactating or pregnant female will not be eligible for participation or continuation in this study.

